## METHODS AND PROCEDURES

**Study Design:** Describe the research design, including a description of any new methodology and its advantage over existing methodologies.

A 14 week, randomized, double-masked, placebo controlled trial in 40 participants.

This study will be performed at the University of Vermont and Duke University. Two centers will facilitate recruitment, and improve generalizability of findings to inform any decision to proceed with a full-scale, appropriately powered multi-center trial.

### **Background Asthma Care**

Participants will be treated in accordance with asthma guidelines and best practices using materials already developed at our centers. All participants will be prescribed controller medication that includes inhaled corticosteroids and additional add-on treatments as needed.

**Rationale for study duration:** We based the duration of the study on the likely time needed to improve asthma control, and to determine the tolerability of the supplement over several weeks.

### **Source of Study Medication**

MitoQ capsules and placebo will be provided by MitoQ Ltd.

### **Rationale for dose of active supplement:**

The dose of supplement will be 40 mg per day, which is based on tolerability and efficacy findings in prior human studies (references 6-8 listed above). Participants will be started on 20 mg a day for at least the first three days and will then be escalated to 40 mg if well tolerated.

### **Randomization and blinding:**

Treatment assignments will be stratified by center and the allocation ratio will be (1:1). Randomization will be accomplished by reviewing and confirming eligibility data; after verification of eligibility, a treatment assignment number corresponding to a unique study kit will be assigned. Study kits will be labeled with two-part tear-off labels with unique identifiers. The tear-off label will be affixed to a study form when the kit is assigned to a participant and the information will be keyed into data system to verify that assigned treatment was given to the participant.

**Procedures:** Describe all procedures (sequentially) to which human participants will be subjected. Identify all procedures that are considered experimental and/or procedures performed exclusively for research purposes. Describe the types, frequency and duration of tests, study visits, interviews, questionnaires, etc. Include required screening procedures performed before enrollment and while on study. Please provide in table, list or outline format for ease of review. (describe and attach all instruments)

Note: A clinical research protocol may involve interventions that are strictly experimental or it may involve some aspect of research (e.g., randomization among standard treatments for collection and analysis of routine clinical data for research purposes). It is important for this section to distinguish between interventions that are experimental and/or carried out for research purposes versus those procedures that are considered standard therapy. In addition, routine procedures performed solely for research purposes (e.g., additional diagnostic/follow-up tests) should be identified.

All procedures will be performed exclusively for research purposes.

Due to COVID-19 some of these procedures may not occur until guidelines allow it.

COVID testing and other precautions will be conducted according to current institutional guidelines.

Outline of Study Visits							
Week	-2	0 +/- 3 days	3 days after V2 +3 days	2 +/- 3 days	6 +/- 10 days	1-10 days prior to V5b	12 +/- 10 days
Visit number	V1	V2	Phone call ∞	V3 ∞	V4 ∞	V5a ∞	V5b ∞
Consent	*						
Baseline/interim history	*	*	*	*	*	*	*
Concomitant medication review	*	*		*	*	*	*
Collect and review diary cards		*		*	*		*
Treatment assignment (randomization)		*					
Drug distribution		*			*		
Drug titration			*				
Drug return/ Pill counts				*	*		*
Assess for adverse events		*	*	*	*	*	*
Spirometry	*¥	* €				*€	*€
Forced oscillation	*	*				*	*
Lung Volumes	*						
Induced sputum	*					*‡	
Exhaled breath condensate	*	*					*
Exhaled nitric oxide	*	*					*
Methacholine Challenge		*^					*
Nasal lavage & nasal brush	*	*					*
Nasal strip	*	*				*	*
Asthma Control (ACT)	*	*		*	*		*
Marks AQLQ	*	*		*	*		*
ASUI	*						
Anthropometrics	*	*		*	*		*
Temperature	*	*					*
Blood pressure	*	*				*	*
Blood draw†	*	Fasting		Fasting	Fasting	Fasting	
Urine sample	*	*		*	*	*	*
Pregnancy test*	*	*		*	*	*	*
Follow-up phone call			*				
End of study questionnaire							*
Follow-up visit+	*	*				*	*

\*for women of child-bearing potential

¥V1 spirometry only will be performed pre and post bronchodilator

†fasting blood draw may be performed on a different day ( $\pm 7$  days of actual visit)

‡Induced sputum at V5 will be performed within 10 days prior to the other V5 procedures (induced sputum and methacholine cannot be done at same visit, both may cause bronchoconstriction)

^participants with a negative methacholine test will stop visit 2 early

†follow-up visits will be scheduled in the event that a lung test cannot be performed that day

€ spirometry is done as part of the induced sputum or methacholine procedure

∞Visit windows for the visits following visit 2 will be scheduled based off of the date the participant was randomized to study drug

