### Secondary outcomes

- ◆ Change in mitochondrial reactive oxygen species in nasal epithelial cells.
- ◆ Change in sputum, nasal lavage, serum and exhaled breath 8-isoprostanes.
- ◆ Change in induced sputum cell counts.
- ◆ Changes in asthma control documented with daily asthma diaries (including symptoms, rescue medication use, and peak flow measurements).
- ◆ Adherence monitored in daily asthma diary cards and by pill counts.
- ◆ The Asthma Control Test (ACT), a 4-week recall questionnaire that measures asthma control.
- ◆ The Marks Asthma Quality of Life Questionnaire (Marks AQLQ), an asthma-specific quality of life questionnaire.
- ◆ The Asthma Symptom Utility Index (ASUI), a 2-week utility-weighted asthma symptom questionnaire.
- ◆ Anthropometrics will include height and weight, and hip and waist measurements.
- ◆ Spirometry with bronchodilator will be performed to measure FEV1 and FVC in accordance with ATS/ERS standards.
- ◆ Forced oscillation (with methacholine testing) will be used to measure impedance, detect changes in the periphery of the lung.
- ◆ Adverse effects will be assessed by open-ended questions at each visit and rated in severity.
- ◆ Interval health history will be recorded at each clinic visit.
- ◆ Baseline questionnaires and exam will be administered to ascertain demographics, including self-reported ethnicity and race, general health, co-morbid conditions, asthma symptoms, and medication use.
- ◆ Exit questionnaires will be administered at the last visit to determine global assessments of treatment, adequacy of informed consent procedures, satisfaction with study procedures and personnel, and opinions about the intervention.

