#### Visit 2 (duration 2 to 3 hours)

Participants will have fasting blood drawn for blood glucose, CBC w/ differential, CMP, and collection of serum and plasma for research (this may also be scheduled within 7 days per participant preference), assess for adverse events, obtain weight, measure blood pressure, temperature, review concomitant medications, obtain interim medical history, collect and review diary cards, perform spirometry, and perform a methacholine challenge test (measuring response by both FEV1 and forced oscillation). If we are unable to obtain sputum from the participant at visit 1 we will see if the participant is able to produce sputum spontaneously during pulmonary function testing. We will collect urine for research. Women of childbearing potential will perform a urine pregnancy test. We will collect exhaled breath condensate and exhaled nitric oxide measurement. We will insert a nasal strip for sample collection, then perform nasal lavage, and collect nasal cells via nasal brush. Participants will complete questionnaires about asthma control and asthma quality of life. Participants will be randomized to study medication and study drug will be dispensed.

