#### Visit 5a (duration 1.5 hours)

We will schedule the induced sputum prior to other study procedures (within 10 days of V5). We will assess for any adverse events, measure blood pressure, perform forced oscillation, obtain spontaneous sputum or perform the induced sputum procedure, review concomitant medications, and obtain an interim medical history. We will insert a nasal strip for sample collection. We will collect urine for research. Women of childbearing potential will perform a urine pregnancy test. Participants will have fasting blood drawn for

blood glucose, CBC w/ differential, CMP, and collection of serum and plasma for research (this may also be scheduled within 7 days per participant preference).

Visit 5b (duration 3 hours)

We will collect and review diary cards and assess adherence to study medication (by pill count). We will collect all remaining study drug. We will perform nasal lavage, collect nasal cells via nasal brush, measure blood pressure, temperature, obtain weight, and hip and waist circumference. Participants will perform spirometry. We will insert a nasal strip for sample collection. We will collect urine for research. Women of childbearing potential will perform a urine pregnancy test. We will perform a methacholine challenge test with forced oscillation (measuring response by both FEV1 and forced oscillation). If we are unable to obtain sputum from the participant at visit 5a we will see if the participant is able to produce sputum spontaneously during pulmonary function testing. We will collect exhaled breath condensate and exhaled nitric oxide. Participants will complete questionnaires about asthma control and asthma quality of life, and an end of study participant questionnaire.

Additional visit:

Some participants may be asked to return for an additional visit if some of the tests were not completed at the regular scheduled visits or for unexpected events. This additional visit may involve spirometry, a methacholine challenge, or induced sputum depending on the need for the specific participant. The participant's blood pressure will be assessed if the methacholine challenge or induced sputum need to be performed. In addition, women of childbearing potential will be required to undergo a urine pregnancy test prior to testing.

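### The ±7-day fasting-blood window allows an on-drug V2 sample and an off-drug end sample, which can shrink the measured change in serum 8-isoprostanes

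*Combined protocol and SAP*

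**What the plan says.** - **The window.** The Outline of Study Visits marks the blood draws at V2, V3, V4 and V5a as fasting. A footnote states that the "fasting blood draw may be performed on a different day", with a margin of 7 days on either side. The Visit 2 text repeats the allowance ("this may also be scheduled within 7 days per participant preference"), as do the texts for V3, V4 and V5a.
- **Start of drug.** Visit 2 ends with this step: "Participants will be randomized to study medication and study drug will be dispensed". Under Rationale for dose, "Participants will be started on 20 mg a day for at least the first three days and will then be escalated to 40 mg", if tolerated. The visit table puts the titration call at "3 days after V2 +3 days".
- **End of drug.** V5a falls "1-10 days prior to V5b". At V5b, "We will collect all remaining study drug". The Venipuncture section confirms that V5b has no blood draw.
- **Outcome.** The secondary outcomes include "Change in sputum, nasal lavage, serum and exhaled breath 8-isoprostanes".
- **Other pre-treatment blood.** V1 collects CBC, CMP, serum and plasma before any drug. It is not marked fasting, and its text does not list blood glucose.
- **Analysis.** The Analysis Plan describes end-of-study group comparisons, a mixed model for change from baseline, and a mixed model with categorical time for measures taken repeatedly. It does not say which sample is the serum baseline. It has no rule for the actual draw date relative to first or last dose.

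**The concern.** A window that is the same on both sides does no harm while exposure is constant, as at V3 and V4. At V2 and V5a exposure changes. A late V2 draw measures a participant already taking study drug. A late V5a draw measures one who has given the drug back. In the active arm, either can remove part of a drug effect from the measured change, while the placebo arm has no drug effect to lose. Serum 8-isoprostane is one of the trial's readouts of the proposed oxidative-stress mechanism. With about 20 participants per arm, a few shifted samples could matter to how that result is read.

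**Working it through.** **1. Number of draws (the protocol's own figure).** The Venipuncture section gives 30 cc at every visit except V5b. The visits are V1, V2, V3, V4 and V5a: 30 × 5 = 150 cc, which matches the stated total. V5a is therefore the only end-of-treatment blood sample.

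**2. V2 draw.** Day 0 ± 7 gives day −7 to day +7. Of 15 permitted days, 7 fall after randomization. The titration call is on day 3 to day 3 + 3 = 6, so a day-7 draw can follow the dose step.

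**3. Crossing windows.** The V3 visit is day 14 ± 3, that is 11 to 17. With ± 7 the draw is day 4 to 24. A V2 draw on day 7 can come later than a V3 draw on day 4.

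**4. V5a draw relative to V5b.** The visit is 1 to 10 days before V5b.
- Earliest draw: −10 − 7 = −17 days. Latest: −1 + 7 = +6 days.
- A draw after V5b needs V5a to be 6 days or less before V5b. Counting lag by offset: 6 + 5 + 4 + 3 + 2 + 1 = 21 of 10 × 15 = 150 combinations (14%). Another 7 fall on the day of V5b.
- These are counts of permitted days, not predicted frequencies.

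**5. Possible attenuation (assumed kinetics).** The documents give no onset or offset times for serum markers. Assume exponential onset and offset with half-life h days, dosing from day 0 to day 84.
- Effect present at a day-7 V2 draw: f = 1 − 2^(−7/h)
- Effect remaining 6 days after stopping: g = (1 − 2^(−84/h)) × 2^(−6/h)
- Share of the effect left in the V2-to-end change: g − f. With only the V2 draw late: (1 − 2^(−84/h)) − f.

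| Share of effect left | h = 3 | h = 7 | h = 14 |
|---|---|---|---|
| f (already present at day 7) | 0.80 | 0.50 | 0.29 |
| g (left 6 days off drug) | 0.25 | 0.55 | 0.73 |
| Latest draw at V2 only | 0.20 | 0.50 | 0.69 |
| Latest draw at both ends | −0.55 | 0.05 | 0.44 |
| All permitted days equally likely | 0.68 | 0.82 | 0.88 |
| V1 as baseline, latest V5a draw | 0.25 | 0.55 | 0.73 |

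The latest-draw rows describe a participant whose draws fall at the limits, not a group mean.

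**6. Share of participants affected.** If a share p of the active arm draws V2 late and shows a fraction f of the effect by then, the mean change loses p × f: 0.25 × 0.25 = 6%, 0.5 × 0.5 = 25%, 0.75 × 0.75 = 56%. All values of p and f are assumptions.

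**The case against.** The case on the other side is substantial, and much of it stands.

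- **Permission is not occurrence.** A reader might infer that the serum results are biased toward no effect, or that a true effect would read as none. The documents do not support that. The Visit 2 text lists blood first and randomization last, and moving the draw is optional. How often it happens and how fast the marker moves are both unknown. Even p = f = 0.75 leaves 44% of the effect.
- **V1 is a real fallback.** A reader might infer that the pre-treatment safety reference is lost. It is not, because V1 supplies drug-free CBC and CMP as well as serum. Nothing says that 8-isoprostane must be measured fasting. What V1 lacks is a sample marked fasting and a listed glucose test, and glucose is not a listed outcome.
- **V2 is nowhere named as the serum baseline.** The gap is that the baseline sample is undefined.
- **Not every analysis is exposed.** A late V2 draw leaves end-of-study group comparisons untouched. V3 and V4 samples also inform the repeated-measures model.
- **Day +1 may precede the first dose.** The Toxicity section has the capsule taken after an overnight fast, and the time of the first dose is not fixed.
- **The V5a problem is an edge case.** It needs a short V5a-to-V5b gap and a return for blood after the final visit.

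Two things survive all of this. No rule ties either draw to first or last dose, and V1 does nothing for a late V5a sample.

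**Conclusion.** The concern holds as a gap in what the plan permits, not as a demonstrated bias. A compliant V2 draw can be up to 7 days after dispensing, and a compliant final draw up to 6 days after drug return. If draws are moved late and the marker changes within days, the V2-to-end change in serum 8-isoprostanes is attenuated in the active arm. The size depends on figures that the documents do not give. Under the assumed half-lives, with all permitted days equally likely, 12% to 32% of the effect is lost (1 − 0.88 to 1 − 0.68).

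The reach is narrow: one of the four 8-isoprostane sample types, plus the fasting glucose, CBC and CMP taken at the same draws. The methacholine outcome and the nasal, breath and sputum measures do not use this window. The timing limits are certain and the amount of bias is not. The change is worth making because it is cheap, not because the trial's main conclusion depends on it.

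**What to change.** 1. Make the window one-sided at two draws. Take the V2 fasting sample on day −7 to day 0 and before the first dose of study drug. Take the V5a fasting sample no later than V5b and before study drug is returned. Keep ±7 days for V3 and V4.
2. Name the serum baseline in the Analysis Plan: V2 if drawn before the first dose, otherwise V1.
3. Record the dates of each draw, the first dose and the last dose.
4. For samples already drawn outside these limits, use V1 as the baseline where V2 was late, and add a sensitivity analysis without the out-of-limit samples. Do not drop them from the main analysis, since that would be an exclusion after randomization driven by participants' scheduling in a 40-person trial.

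The cost is a footnote and a few lines in the Analysis Plan, with slightly less scheduling flexibility at two draws. Some fasting samples may be taken from people who then have a negative methacholine test at V2, although the Visit 2 text already lists blood ahead of that test. No extra visits, samples or participants are needed.

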#### Visit 1 (duration three to four hours)

We will obtain informed consent, a baseline medical history, concomitant medications, and measure blood pressure, temperature, height, weight, and waist and hip circumference. We will collect urine for research. Women of childbearing potential will perform a urine pregnancy test. Participants will have blood drawn for an IgE, CBC w/ differential, CMP, and collection of serum and plasma for research. We will perform spirometry with bronchodilator, lung volumes, forced oscillation, and then induce sputum spontaneously or with inhaled hypertonic saline. We will collect exhaled breath condensate and exhaled nitric oxide measurement. We will insert a nasal strip for sample collection, then perform nasal lavage, and collect nasal cells via nasal brush. Participants will complete questionnaires pertaining to asthma control and asthma quality of life. We will instruct participants how to fill out asthma diary cards.

#### Visit 2 (duration 2 to 3 hours)

Participants will have fasting blood drawn for blood glucose, CBC w/ differential, CMP, and collection of serum and plasma for research (this may also be scheduled within 7 days per participant preference), assess for adverse events, obtain weight, measure blood pressure, temperature, review concomitant medications, obtain interim medical history, collect and review diary cards, perform spirometry, and perform a methacholine challenge test (measuring response by both FEV1 and forced oscillation). If we are unable to obtain sputum from the participant at visit 1 we will see if the participant is able to produce sputum spontaneously during pulmonary function testing. We will collect urine for research. Women of childbearing potential will perform a urine pregnancy test. We will collect exhaled breath condensate and exhaled nitric oxide measurement. We will insert a nasal strip for sample collection, then perform nasal lavage, and collect nasal cells via nasal brush. Participants will complete questionnaires about asthma control and asthma quality of life. Participants will be randomized to study medication and study drug will be dispensed.

#### Follow-up phone call (duration 10 minutes)

We will assess for symptoms to determine if the participant should increase to two tablets (40 mg) of study drug a day, remain at 1 tablet (20 mg) a day, or withdraw from treatment. We will also assess for study drug adherence, assess if vaping and/or inhaling marijuana, and any other adverse events.

#### Visits 3 (duration 1 hour)

We will assess for any adverse events, obtain weight, review concomitant medications, and obtain interim medical history. We will collect and review diary cards and assess adherence to study medication (by pill count). Participants will have fasting blood drawn for blood glucose, CBC w/ differential, CMP, and collection of serum and plasma for research (this may also be scheduled within 7 days per participant preference). We will collect urine for research. Women of childbearing potential will perform a urine pregnancy test. Participants will complete questionnaires about asthma control and asthma quality of life.

#### Visits 4 (duration 1 hour)

We will assess for any adverse events, obtain weight, review concomitant medications, and obtain interim medical history. We will collect and review diary cards and assess adherence to study medication (by pill count). Study drug will be collected and new drug will be dispensed. Participants will have fasting blood drawn for blood glucose, CBC w/ differential, CMP, and collection of serum and plasma for research (this may also be scheduled within 7 days per participant preference). We will collect urine for research. Women of childbearing potential will perform a urine pregnancy test. Participants will complete questionnaires about asthma control and asthma quality of life.

#### Visit 5a (duration 1.5 hours)

We will schedule the induced sputum prior to other study procedures (within 10 days of V5). We will assess for any adverse events, measure blood pressure, perform forced oscillation, obtain spontaneous sputum or perform the induced sputum procedure, review concomitant medications, and obtain an interim medical history. We will insert a nasal strip for sample collection. We will collect urine for research. Women of childbearing potential will perform a urine pregnancy test. Participants will have fasting blood drawn for

blood glucose, CBC w/ differential, CMP, and collection of serum and plasma for research (this may also be scheduled within 7 days per participant preference).

Visit 5b (duration 3 hours)

We will collect and review diary cards and assess adherence to study medication (by pill count). We will collect all remaining study drug. We will perform nasal lavage, collect nasal cells via nasal brush, measure blood pressure, temperature, obtain weight, and hip and waist circumference. Participants will perform spirometry. We will insert a nasal strip for sample collection. We will collect urine for research. Women of childbearing potential will perform a urine pregnancy test. We will perform a methacholine challenge test with forced oscillation (measuring response by both FEV1 and forced oscillation). If we are unable to obtain sputum from the participant at visit 5a we will see if the participant is able to produce sputum spontaneously during pulmonary function testing. We will collect exhaled breath condensate and exhaled nitric oxide. Participants will complete questionnaires about asthma control and asthma quality of life, and an end of study participant questionnaire.

Additional visit:

Some participants may be asked to return for an additional visit if some of the tests were not completed at the regular scheduled visits or for unexpected events. This additional visit may involve spirometry, a methacholine challenge, or induced sputum depending on the need for the specific participant. The participant's blood pressure will be assessed if the methacholine challenge or induced sputum need to be performed. In addition, women of childbearing potential will be required to undergo a urine pregnancy test prior to testing.

**For research involving survey, questionnaires, etc.:** *Describe the setting and the mode of administering the instrument and the provisions for maintaining privacy and confidentiality. Include the duration, intervals of administration, and overall length of participation. (describe and attach all instruments)*

